There are limitations to the use of AL which is the commonly used ACT in Nigeria. These include high number of dosing (six) which is not convenient and the need to give the drug with fatty food for optimal absorption of lumefantrine because of its high lipophilic property.[19] Pyronaridine, a Mannich base 1-aza-acridine structurally related to mepacrine and amopyroquine, one of the earliest synthetic antimalarial drugs, was first developed in China over 30 years ago. It has been used as monotherapy in parts of Asia and China.[20] Pyronaridine, is a benzonaphthyridine derivative that is active against *Plasmodium falciparum* and *Plasmodium vivax*.[21, 22]¹⁴

Pyronaridine-Artesunate (PA) is a novel fixed dose ACT drug that received a Positive Opinion through Article 58 from the **European Medicine Agency¹ (EMA)**. This Positive Opinion is a stringent regulatory review and approval granted for a specific group of drugs that will not be marketed in Europe. This rigorous review process is performed in conjunction with the WHO. At the time of the Positive Opinion (registration) PA also obtained WHO prequalification status. Pyramax received approval with EMA for the treatment of acute uncomplicated *P. falciparum* and *P. vivax* malaria. Subsequent EMA approvals have been granted for repeated dosing and for the paediatric formulation of granules in sachets. pyronaridine-artesunate has been found to have good efficacy and tolerability and is cost effective.[23-26] Like DP, pyronaridine-artesunate has a daily dosing regimen and can be taken with or without meals.[23] The studies conducted so far on the efficacy and tolerability of PA showed that other ACTs were not superior to it and there were strong recommendations that PA should be included as a standard antimalarial treatment.[27] The most commonly reported adverse effects were headache, eosinophilia, neutropenia, anaemia, increased platelet count, vomiting, abdominal pain, bradycardia, short lasting transaminase increases and hypoglycaemia.¹⁶ Other studies reported vomiting which may be due to its bitter taste, nausea, loss of appetite and cough.[27] More recent studies provide increasing evidence on the safety of Pyramax.[28, 29]

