The first, third and fifth doses will be administered supervised in the clinic with water (very young children or a glass of milk while the second, fourth and sixth doses will be given by the care-giver at home 8 hours and 12 hours respectively after the first and subsequent morning doses. Mothers will be encouraged to breastfeed very young babies still on the breast soon after drug administration. Parent/guardian will be provided a sachet of milk after consultation on days 0, 1 and 2 for the 2nd, 4th and 6th doses of AL. Parents and care-givers will be also advised to give Coartem™ with a fatty meal e.g. fried plantain or bean porridge (local fatty meals) for the older children especially those who cannot tolerate milk.

Each enrollee will then be observed in the clinic for 1 hour after drug administration for vomiting. If vomiting occurs within 30 minutes of drug administration, the full treatment dose (PA or AL) will be re-administered. If vomiting occurred between 30-60 minutes of drug administration, half the treatment dose will be re-administered. Any enrollee who vomits the repeat dose will be withdrawn from the study and treated with another ACT.

No other antimalarial therapy will be allowed/given throughout the study period (28 days) except there is parasite recurrence. Paracetamol – an antipyretic drug will be administered to study participants with axillary temperatures ≥38.5°C at standard dosage.

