- **Gametocyte carriage**: proportions of patients with gametocyte at a given point in time using the Area Under the Curve Graph for PA will be compared with that of AL.

3.7.3 Safety parameters will be evaluated as follows:

- Safety will be analyzed in terms of adverse events and severe adverse events using clinical signs, symptoms and laboratory parameters.
- Liver enzymes (ALT/AST) >3 times upper limit of normal (ULN) plus peak total bilirubin >2 times ULN in the absence of a significant alkaline phosphatase increase (= Hy's law) will be deemed as serious adverse effects (SAE).
- ALT and AST >5 times ULN will be deemed an AESI. (see below)

Serious Adverse Events

An adverse event will be considered serious if it fulfils one of the following criteria:

- causes death or
- is life-threatening or necessitates hospitalization or prolongs hospitalization or results in persistent or significant disability/incapacity or is a medically important event constitutes a possible Hy's Law

An example of an important medical event is one that while not-immediately life-threatening might become so if there had been no intervention

In case of SAEs, independent of causality, the healthcare personnel must immediately contact the PI / Investigator for validation of the seriousness and determination of the causality.

Subsequently, the procedure described below must be followed:

- SEND (within 24 hours and pdf scanned documents) the signed and dated copy of the “Adverse Event form” and the form “SAE complementary information” to Shin Poong Pharmacovigilance (PV) (Tel/[contact] or email: [contact])
- Contact immediately (the same day) the medical monitor/Pyramax QPPV responsible for safety in case of death or life-threatening events.
- The follow-up of each fatal or life-threatening AE must be provided to the medical monitor and Shin Poong PV within the same timeline as the initial report (within 24 hours and preferably by email).
- ATTACH to the Case Record Form (CRF) the photocopy of all available results and examinations which were undertaken (and their date). Analysis results must be accompanied by the laboratory normal ranges. Special consideration shall be taken to ensure patient anonymity, and to the correct completion of the patient’s study specific identifier in the copies of the source documents provided to the sponsor.

Causality

All adverse events must have causality assigned by the investigator. As a guide causality can be assigned as follows:

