Address (+ brief description):
.....
.....
.....

Symptoms History

Record duration of symptoms in days (Today = 1) Fever: () Vomiting: () Chills & rigors ()

Diarrhoea: () Headache: () Abdominal pains: () Irritability: () Loss of appetite ()

Other complaint 1: Other complaint 2:

Past medical history:

History of drug allergy: (Yes/No) If yes, name of drug:

Any other relevant history 1:

Any other relevant history 2:

Treatment history: Has the child received any of the following drugs in the last 2 weeks (Yes/No)

CQ () SP () PCM () ACT () Specify.....

Antibiotic () Specify..... Other:

Clinical examination:

General: Palor (Yes/No) Icterus (Yes/No) Fever (Yes/No) Dehydration (Yes/No)

CVS: Pulse/min..... Apex Beat..... Heart sounds.....

Respiratory system: Resp. rate..... Breath sound.....

Abdomen: Liver size (Below costal margin)..... Spleen size..... Kidneys.....

Muscle tone: (1) Normal (2) Hypotonia (3) hypertonia Eyes: conjunctivitis/Discharge (Yes/No)

Ears: Discharge (Yes/No)

MP result: PCV.....

**PYRONARIDINE-ARTESUNATE VERSUS ARTEMETHER-
LUMEFANTRINE STUDY**

Study ID- PAAL:

Study ID -----

Study Drug Schedule

| Study Day | Date | Drug [PA or AL] Name of Drug | Dose | Time Drug Given |
|------------------|-------------|---|-------------|------------------------|
| Day 0 | | | 1st | |
| | | | 2nd | |
| Day 1 | | | 1st | |
| | | | 2nd | |
| Day 2 | | | 1st | |
| | | | 2nd | |

Comments:

Any vomiting? Yes/No

Time

Any Redosing?

Time

Any vomiting? Yes/No

Any other comments

CLINICAL FOLLOW UP RECORD

| | D0 | D1 | D2 | D3 | D7 | D14 | D21 | D28 | Day 35 | Day 42 | Other visit |
|---------------------------|-----------|-----------|-----------|-----------|-----------|------------|------------|------------|---------------|---------------|--------------------|
| Date | | | | | | | | | | | |
| Temp (°C) | | | | | | | | | | | |
| Pallor | | | | | | | | | | | |
| Jaundice | | | | | | | | | | | |
| HR/Pulse Rate | | | | | | | | | | | |
| Resp Rate | | | | | | | | | | | |
| Lung Fields | | | | | | | | | | | |
| Liver (cm) | | | | | | | | | | | |
| Spleen (cm) | | | | | | | | | | | |
| Weight (kg) | | | | | | | | | | | |
| PCV (%) | | | | | | | | | | | |
| Parasite Density/ μ L | | | | | | | | | | | |
| Gametocyte Count/ μ L | | | | | | | | | | | |

TREATMENT EMERGENT SIGNS AND SYMPTOMS (TESS)

| Features | Day 0 | | Day 1 | | Day 2 | | Day 3 | | Day 7 | | Day 14 | | Day 21 | | Day 28 | | Day 35 | | Day 42 | | Extra Visit | | Extra Visit | | |

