|---------------|-------|---|-------|---|-------|---|-------|---|-------|---|--------|---|--------|---|--------|---|--------|---|--------|---|-------------|---|-------------|---|--|
| | P | S | P | S | P | S | P | S | P | S | P | S | P | S | P | S | P | S | P | S | P | S | P | S | |
| Date | | | | | | | | | | | | | | | | | | | | | | | | | |
| Chills/Rigors | | | | | | | | | | | | | | | | | | | | | | | | | |
| Fever | | | | | | | | | | | | | | | | | | | | | | | | | |
| Anorexia | | | | | | | | | | | | | | | | | | | | | | | | | |
| Nausea | | | | | | | | | | | | | | | | | | | | | | | | | |
| Vomiting | | | | | | | | | | | | | | | | | | | | | | | | | |
| Diarrhoea | | | | | | | | | | | | | | | | | | | | | | | | | |
| Abd. Pains | | | | | | | | | | | | | | | | | | | | | | | | | |
| Cough | | | | | | | | | | | | | | | | | | | | | | | | | |
| Palpitation | | | | | | | | | | | | | | | | | | | | | | | | | |
| Insomnia | | | | | | | | | | | | | | | | | | | | | | | | | |

Present (P): 0 = Not present, 1= Present, 2 = Not evaluable

Severity (S): 1 = Mild 2 = Moderate 3 = Severe

TREATMENT EMERGENT SIGNS AND SYMPTOMS (TESS)

| Features | Day 0 P S | | Day 1 P S | | Day 2 P S | | Day 3 P S | | Day 7 P S | | Day 14 P S | | Day 21 P S | | Day 28 P S | | EXTRA VISIT | |
|-------------|-----------------|--|-----------------|--|-----------------|--|-----------------|--|-----------------|--|------------------|--|------------------|--|------------------|--|----------------|--|
| Date | | | | | | | | | | | | | | | | | | |
| Pallor | | | | | | | | | | | | | | | | | | |
| Yellow eyes | | | | | | | | | | | | | | | | | | |
| Headaches | | | | | | | | | | | | | | | | | | |
| Rash | | | | | | | | | | | | | | | | | | |
| Reflex | | | | | | | | | | | | | | | | | | |
| Diplopia | | | | | | | | | | | | | | | | | | |
| Fatigue | | | | | | | | | | | | | | | | | | |
| Other | | | | | | | | | | | | | | | | | | |
| Other | | | | | | | | | | | | | | | | | | |

Present (P): 0 = Not present, 1= Present, 2 = Not evaluable

Severity (S): 1 = Mild 2 = Moderate 3 = Severe

.....
LABORATORY RESULTS: LFT & BLOOD CHEMISTRY

| PARAMETER | DAY 0 | DAY 3 | DAY 7 | DAY 27 | DAY 35 | DAY 42 |
|----------------------|-------|-------|-------|--------|--------|--------|
| Date | | | | | | |
| Urea | | | | | | |
| Creatinine | | | | | | |
| Random Blood sugar | | | | | | |
| Total bilirubin | | | | | | |
| Conjugated bilirubin | | | | | | |
| ALT | | | | | | |
| AST | | | | | | |
| ALP | | | | | | |

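### The symptom sheets have a single Day 0 column, not marked as before or after the first dose, and no rule for what counts as treatment-emergent

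*Combined protocol and SAP*

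**What the plan says.** Comparing safety is part of the stated aim (section 2). Section 3.7.3 states the safety analysis in one sentence: "Safety will be analyzed in terms of adverse events and severe adverse events using clinical signs, symptoms and laboratory parameters". Neither that section nor the Data Analysis section defines treatment-emergent or says how Day 0 symptom entries are to be used.

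The case record form has two sheets headed "TREATMENT EMERGENT SIGNS AND SYMPTOMS (TESS" (TESS below). Both give Day 0 a single visit column; their header rows begin "Features | Day 0 | | Day 1 | | Day 2" and "Features | Day 0 P S | | Day 1 P S". The coding key is "Present (P): 0 = Not present, 1= Present, 2 = Not evaluable", plus a three-level severity grade. There is no onset time and no code for new or worse than before.

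Three other parts of the form bear on Day 0:

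- The Symptoms History taken at enrolment, with the instruction "Record duration of symptoms in days (Today = 1".
- The Study Drug Schedule page, which has a vomiting and re-dosing block with times.
- The Adverse Events Record, which has columns for Days 0, 3, 7 and 28 and for extra visits.

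Section 3.7.1 adds: "Each enrollee will then be observed in the clinic for 1 hour after drug administration for vomiting". Of PA, the Introduction says: "Other studies reported vomiting which may be due to its bitter taste, nausea, loss of appetite and cough".

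**The concern.** Every child enters with symptoms of malaria (section 3.6.1), and many TESS rows, such as fever, chills, vomiting, anorexia and headache, are also presenting symptoms. On Day 0 the same child has a pre-dose state and a post-dose state. The form has one cell for presence and one for severity, and does not say which state they describe. Staff may complete the column differently from child to child, and the analyst could not tell which was done.

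At stake is the symptom comparison on the first dosing day and, for rows without an enrolment field, the baseline for every later visit. Two of the four effects that the Introduction lists together for PA, nausea and cough, are among those rows. A baseline that was never recorded cannot be rebuilt in analysis.

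**Working it through.** The plan gives no tolerability figure to reproduce. The check is mainly a comparison of the form's pages, followed by a short illustration.

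**1. Rows with a pre-dose record elsewhere.** TESS names 17 symptoms or signs: 10 on the first sheet and 7 on the second, apart from two blank lines. Matching them to the enrolment history and examination gives:

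- Dedicated enrolment field, 9 rows: chills/rigors, fever, anorexia, vomiting, diarrhoea, abdominal pains, headaches, pallor, yellow eyes.
- No dedicated field, 8 rows: nausea, cough, palpitation, insomnia, rash, reflex, diplopia, fatigue. Only two free-text complaint lines could hold these.

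The Symptoms History records duration and the examination records yes/no for pallor and icterus. Neither records severity.

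**2. The two ways of completing Day 0.**

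- *Before the first dose.* TESS then holds a graded baseline for all 17 rows and nothing is diluted. First-dose reactions have no graded cell. Vomiting has its item on the dosing page; other reactions wait for the Day 1 history.
- *After the first dose.* There is no graded baseline. For the 9 rows, absent at enrolment and present on Day 0 gives new onset, but worsening cannot be derived. For the 8 rows, neither can be derived reliably.

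**3. Whether other pages fill the gap.**

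- The vomiting block is timed, but it is one block for six dose rows over three days, with no day or dose label and no grade.
- The Adverse Events Record also has one Day 0 column, no onset or severity field, and no Day 1 or Day 2 column.
- The visit history in section 3.7.2 may recover some reactions on Day 1, but nothing requires them to be dated to the first dose.

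**4. What follows if raw Day 0 presence is counted as an event.** Let a share b of each arm have the symptom before dosing, and let r be the rate of new onset among the rest. Then

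observed rate = b + (1 − b)r, so observed difference = (1 − b)(r_PA − r_AL).

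The documents give no value for b or r. As an assumed example, take r = 15% (PA) against 5% (AL) and 84 per arm (section 3.6). For b = 0.3, PA is 0.3 + 0.7 × 0.15 = 0.405 and AL is 0.3 + 0.7 × 0.05 = 0.335, a difference of 0.07.

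Power at two-sided 5% is Φ{[|p1 − p2|√n − 1.96√(2p̄(1 − p̄))] / √[p1(1 − p1) + p2(1 − p2)]}. For b = 0.3 this is (0.642 − 1.338)/0.681 = −1.02, or 15%. The last column of the table instead drops children who already had the symptom, so that n = 84(1 − b) per arm and the difference stays at 10 points.

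| b | Raw difference (points) | Power, raw count | Power, new onset only |
|---|---|---|---|
| 0 | 10.0 | 58% | 58% |
| 0.1 | 9.0 | 32% | 54% |
| 0.3 | 7.0 | 15% | 44% |
| 0.5 | 5.0 | 10% | 33% |

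With other assumed rates the pattern is the same. For 20% v 5%, b = 0.5 takes the raw count from 84% to 16%, against 55% for new onset only. For 10% v 3%, the raw count goes from 45% to 7%, against 25%.

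**The case against.** A reader might infer that first-dose emergence cannot be derived at all, and that the trial will therefore tend to report similar tolerability. The documents do not support either statement.

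- The form does not say that the column must hold both states; it is silent. Completed before dosing, it is a sound baseline.
- Nine of the 17 rows have an enrolment field, so new onset can be derived for them if Day 0 is known to be post-dose.
- Vomiting, the most obvious first-dose reaction, depends least on TESS. It has an enrolment field and its own timed item on the dosing page. A power loss worked out for vomiting from TESS Day 0 would describe a count that the form does not force.
- Section 3.7.3 speaks of adverse events, and there is a separate record for them with a Day 0 column. Nothing says that a raw TESS entry is an event.
- The trial is open label, so recording could differ by arm and bias the comparison in either direction.
- Days 1 to 28 have their own columns, and no comparison restricted to Day 0 is planned.

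All of this stands, and it rules out a claim of certain dilution. It does not remove the gap. The column remains unlabelled, severity before dosing is recorded nowhere if Day 0 is completed afterwards, and 8 rows lack a dedicated baseline field. The Adverse Events Record has the same single Day 0 column and less detail.

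**Conclusion.** The point holds in a limited form. TESS leaves the timing of Day 0 undefined, and the plan has no new-or-worsened rule. Depending on when the column is completed, the trial loses either graded first-dose reactions or a graded baseline. In the second case, worsening is lost for all 17 rows and reliable new onset for 8 of them.

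Shrinkage of the PA–AL difference by the factor 1 − b is conditional. It requires that Day 0 is completed after dosing or inconsistently, that raw presence is counted, that the enrolment history is not used, and that recording and pre-dose prevalence are alike in both arms. The rates and powers shown are an assumed illustration, not an estimate of what this trial would lose. This is a cheap improvement to data capture, not a flaw that invalidates the safety comparison.

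**What to change.** Before enrolment starts, split the Day 0 column on both TESS sheets into 'before first dose' and 'after first dose (observed hour)', each with Presence and Severity for every row. Add one derivation rule to the Data Analysis section: a symptom is treatment-emergent only if it was absent before the first dose, or if it is later graded more severe than its pre-dose grade. Apply the rule identically in both arms.

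The cost is one extra form column, or 2 × 17 = 34 more cells per child for the named rows, and one rule. No visit or procedure is added, because the history and examination are already taken at enrolment (section 3.7) and each child is already watched for an hour after dosing (section 3.7.1).

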
**PYRONARIDINE-ARTESUNATE VERSUS ARTEMETHER-
LUMEFANTRINE STUDY**

Study ID- PAAL:

TABLE OF NORMAL VALUES – IBADAN, SOUTHWEST NIGERIA

HAEMATOLOGY

| PARAMETR | NORMAL VALUE | UNIT OF MEASUREMENT |
|---|--------------|---------------------|
| Red Blood Cell Counts | | |
| Male | 4.0 - 6.5 | $\times 10^{12}/l$ |
| Female | 3.5 - 5.5 | $\times 10^{12}/l$ |
| Hemoglobin | | |
| Male | 130 – 180 | g/l |
| Female | 115 - 165 | g/l |
| Packed Cell Volume | | |
| Male | 39 – 54 | % |
| Female | 36 - 46. | % |
| Mean Cell Volume | 80 - 100 | fL |
| Mean Cell Hemoglobin (MCH) | 27 -32 | P/g |
| Mean Cell Hemoglobin Concentration (MCHC) | 300 – 350 | g/l |
| White blood cell count (WBC) | 150 - 350 | $\times 10^9/l$ |
| Platelet count | 90 – 300 | $\times 10^9/l$ |

**PYRONARIDINE-ARTESUNATE VERSUS ARTEMETHER-
LUMEFANTRINE STUDY**

Study ID- PAAL:

LIVER FUNCTION TEST

| PARAMETER | NORMAL RANGE | UNIT OF MEASUREMENT |
|------------------------------------|---------------------|----------------------------|
| Total Bilirubin | 0.2 -1.0 | mg/dl |
| Direct Bilirubin | 0 – 0.4 | mg/dl |
| Alkaline phosphatase (ALP) | 35 - 105 | IU/L |
| Aspartate transaminase (AST) | 0 - 37 | IU/L |
| Alanine transaminase (ALT) | 0 - 40 | IU/L |
| Gamma glutamate transaminase (GGT) | 7 - 50 | IU/L |
| Total protein | 3.5 -8.0 | g/dl |
| Albumin | 3.2 – 5.7 | g/dl |

PLASMA GLUCOSE

| PARAMETER | NORMAL RANGE | UNIT OF MEASUREMENT |
|--------------------------------------|---------------------|----------------------------|
| Fasting plasma glucose | 65 - 110 | mg/dl |
| 2 Hours Post prandial plasma glucose | 60 -140 | mg/dl |

**PYRONARIDINE-ARTESUNATE VERSUS ARTEMETHER-
LUMEFANTRINE STUDY**

Study ID- PAAL:

FASTING LIPID PROFILE

| PARAMETER | NORMAL RANGE | UNIT OF MEASUREMENT |
|-------------------|--------------|---------------------|
| Total cholesterol | <200 | mg/dl |
| Triglyceride | 0 - 200 | mg/dl |
| HDL – Cholesterol | 35 - 86 | mg/dl |
| LDL - Cholesterol | 80 - 120 | mg/dl |

ELECTROLYTE & UREA

| PARAMETER | NORMAL RANGE | UNIT OF MEASUREMENT |
|-------------|--------------|---------------------|
| Sodium | 130 -145 | mmol/L |
| Potassium | 3.5 – 5.0 | mmol/L |
| Chloride | 95 – 110 | mmol/L |
| Bicarbonate | 20 - 30 | mmol/L |
| Urea | 15 - 45 | mg/dl |
| Creatinine | 0.5 – 1.5 | mg/dl |

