3.5 Study Population

The study population will consist of patients with uncomplicated *P. falciparum* malaria attending the study hospital who are aged between 3 and 144 months of age.

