3.7.2 Follow-up

Clinical and parasitological evaluation will be done on each day of follow-up or on any other day if the patient feels unwell. Patients will be reminded by phone calls 30minutes before the next dose of AL and on the day before the follow up visit (all enrollees i.e. PA and AL arms) and those who fail to attend follow up will be visited at home. Transportation fare will be given as incentives to the parents or care givers to encourage attendance for follow up. During each visit, a brief clinical history will be obtained to assess new complaints and possible side effects of medications and a physical examination will also be performed. Hematocrit and chemical analysis (bilirubin, blood glucose, creatinine and liver enzymes- AST, ALT & Alkaline Phosphatase) will be done on at enrolment and follow up on days 3, 7 and 28 to monitor possible changes.

Filter paper blood samples for parasite genotyping will be obtained on day 0, 3, 7, 14, 21 and 28 or earlier if enrollee is symptomatic. A finger prick blood sample will be taken to prepare thick blood smears on days 1, 2, 3, 7, 14, 21, 28 and on any other (unscheduled) visit. The slides will be air-dried away from direct sunlight, stained with fresh 10% Giemsa at pH 7.2 for 15 to 20 minutes and read independently by two microscopists. Parasite density (the number of asexual parasites per μl) will be calculated by counting parasites against about 200 leukocytes and assuming a leukocyte count of 8,000/ μl of blood ³⁶. A smear will be considered negative only after screening at least 200 high power fields. However, a slide will be read against 500 leukocytes before it is declared negative. All discordant smears and slides with a parasite density difference $>10\%$ will be read by an independent microscopist and the PI. For quality control 5% of randomly selected slides will be read by an independent microscopist not involved in the study.

Paired samples (D0 and Day of recurrence) of blood spots on filter paper collected from patients with parasite recurrence on or before D28 will be analyzed using PCR techniques for parasite DNA.

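### The normal white-cell range in the Table of Normal Values cannot be reconciled with the count the protocol assumes elsewhere, and the table lacks neutrophil and eosinophil rows and age bands

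*Combined protocol and SAP*

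**What the plan says.** - **Table of Normal Values, Haematology** (after the reference list). The white-cell row reads "White blood cell count (WBC) | 150 - 350", in units of 10^9/l. The next row, in the same unit, reads "Platelet count | 90 – 300". Haemoglobin is split by sex only: "Male | 130 – 180 | g/l" and "Female | 115 - 165 | g/l". Red cells and packed cell volume are split the same way. No range in the table is split by age, and there is no row for neutrophils or eosinophils.
- **Section 3.7.2.** Parasite density is counted against leukocytes, "assuming a leukocyte count of 8,000" per µl.
- **Section 3.5.** The children are "aged between 3 and 144 months of age".
- **Summary of Activities and CRF.** A full blood count is scheduled on days 0, 3, 7 and 28. The CRF haematology page for those days has rows for total white cells, neutrophils and eosinophils.
- **Introduction**, on PA: "The most commonly reported adverse effects were headache, eosinophilia, neutropenia, anaemia, increased platelet count", followed by further effects.
- **Section 3.7.3.** Safety is to be assessed partly from laboratory parameters. For the documents attached to a serious adverse event report, "Analysis results must be accompanied by the laboratory normal ranges".
- **Data Analysis.** No normal/abnormal category, grade or shift table is defined for haematology.

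**The concern.** Two statements about white cells in the same protocol differ by more than an order of magnitude. The implausible one sits in the only set of normal ranges the document contains. Safety is part of the study aim alongside efficacy, and blood-count changes are among the effects already reported for PA. A reference table that places every child below normal could not show a fall in white cells in one arm.

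The gaps matter for the same reason. The two white-cell subtypes named as known effects have no reference range at all, and nothing says whether the listed ranges are meant for infants, for twelve-year-olds or for adults.

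**Working it through.** A reference range is not derived from other inputs, so there is no planned figure to reproduce. The check is a unit conversion followed by a comparison of the relevant sections.

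**1. Put both white-cell figures in one unit.**
- Assumed count (section 3.7.2): 8,000/µl × 10^6 µl/l = 8.0 ×10^9/l.
- Tabulated range: 150 to 350 ×10^9/l, which is 150,000 to 350,000/µl.

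**2. Take the ratios.**
- Lower limit: 150 / 8 = 18.75.
- Upper limit: 350 / 8 = 43.75.

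The protocol's own working count lies far below its stated lower limit of normal.

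**3. See what each figure implies for the enrolment threshold.** Section 3.6.1 requires at least 1,000 parasites/µl, and section 3.7.2 counts against about 200 leukocytes. Parasites per 200 leukocytes at the threshold = 1,000 × 200 / leukocyte count.
- At 8,000/µl: 25 parasites.
- At 150,000/µl: 1.33 parasites.
- At 350,000/µl: 0.57 parasites.

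The two figures cannot both describe the same children. Density uses the fixed 8,000, so the wrong row does not enter enrolment or efficacy.

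**4. Apply the table literally.** A count is low if it is below 150 ×10^9/l. Values of 2, 4, 8, 11, 15, 20, 30 and 50 ×10^9/l all return low. A child would need 18.75 times the assumed count to reach normal. This holds in either arm and on any day.

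**5. Compare what is recorded with what has a range.**

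| Item | On the CRF | Listed as a PA effect | Range in the table |
|---|---|---|---|
| Total white cells | Yes | Not in the quoted list | Yes, but irreconcilable |
| Neutrophils | Yes | Yes (neutropenia) | None |
| Eosinophils | Yes | Yes (eosinophilia) | None |
| Platelets | Yes | Yes (increase) | Yes, no age band |

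**6. Haemoglobin, as an example of the missing age bands.** The exclusion limit in section 3.6.2 is below 5 g/dl, that is 5 × 10 = 50 g/l. Eligible girls at 50 to 114 g/l and eligible boys at 50 to 129 g/l would fall below the tabulated range at any age from 3 to 144 months. The documents do not say what the limits should be at these ages; they show only that age is ignored.

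**The case against.** The strongest reply is that nothing in the protocol uses this row.

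- **No rule classifies haematology.** The Data Analysis section plans chi-square and t-tests and defines no laboratory flag. The only rules tied to a limit of normal concern liver tests. The sentence on supplying normal ranges belongs to the serious adverse event procedure, covers only results attached to such a report, and refers to the laboratory's ranges without pointing to this table. This stands. A reader might infer that the haematology results will be misclassified, or might multiply four draws by 168 children to get 672 false flags. The documents support neither, because no flagging step exists and the multiplication assumes complete attendance.
- **The 8,000 figure is a counting convention, not a reference range.** This also stands. It shows that the row is wrong but does not supply the right limits.
- **Any wrong flag would fall on both arms, and the raw counts are on the CRF.** Correct. The error does not favour one drug and can be repaired at analysis.
- **The row may be a slip in preparing the table.** Possibly. Label, value and unit line up in the available text, and a look at the source page would settle it. A slip would explain the entry without making it correct.

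A second tempting inference is that the single ALP range of 35 to 105 IU/L would keep children out of the Hy's law rule. The documents do not support it. Section 3.7.3 requires that there be no significant rise in ALP, does not define significant, and does not tie the condition to 105. It can be read as a rise from baseline. The potential Hy's law criterion in section 3.7.4 and the seriousness list in section 3.7.3 carry no ALP condition, so such a case would still be reported. Nor do the documents give paediatric ALP or haemoglobin values from which to judge how many children the limits would misplace.

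**Conclusion.** Wrong as written, and minor. The white-cell row is out by a factor of 18.75 at its lower limit against the protocol's own assumed count; that rests on a unit conversion alone. The missing neutrophil and eosinophil rows and the absence of age bands are plain on the page.

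The consequence depends on the table being used to judge blood counts. If it is, and if the children's counts are anywhere near the assumed 8 ×10^9/l, essentially every white-cell result would be flagged low in both arms. If it is not, the protocol has no stated definition of an abnormal blood count, and that gap also needs closing. Whether the other ranges suit children cannot be decided from the documents. The primary endpoint, parasite density and sample size are untouched.

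**What to change.** 1. Correct the white-cell row against the testing laboratory's own reference range.
2. Add that laboratory's neutrophil and eosinophil ranges.
3. Confirm with the laboratory which ranges apply at 3 to 144 months, using age-specific ranges where it has them.
4. State in the Data Analysis section that these ranges define abnormal haematology results in the safety analysis.
5. Reconcile the Hy's law wording of section 3.7.3, which carries an ALP condition, with section 3.7.4, which does not.

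The cost is one corrected table, a few sentences and a query to the laboratory. The documents do not show whether the laboratory has age-specific ranges, so item 3 may take some follow-up. No visit, sample, endpoint or sample-size change is needed.
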